9.4.2 Secondary outcomes

None

9.5 Data Analyses

For sample descriptive statistics, we will use means and medians for continuous measures, frequencies for count data, and standard deviations and interquartile ranges for variance. For inferential analysis, our primary hypothesis is that milligram morphine equivalent dose will decrease for persons on high doses of opioid therapy.

10. Statistical Analysis

Measures

The primary outcome is average weekly morphine milligram equivalents (MME) prescribed per-clinician. We assessed change in average per-clinician weekly MME from the 34-week baseline period before, to the 34-week period post-intervention using a mixed-effects, knotted spline, left censored regression to account for baseline differences in prescribing, a non-linear change in the rate of opioid prescribing from baseline to post-intervention, and an inflated number of weeks with an average MME of zero, respectively. Predictors include the fixed effects time in weeks, time with a knot at the intervention start, and a random intercept for clinician. The density function to achieve maximum likelihood estimates for a left censored regression is the observed probability of y_i assuming normal distribution ($x_i\beta, \sigma^2$) given that $y_i > 0$, weighted by the probability that y_i is above a censoring threshold, in this case zero.² Because uncensored observations are often skewed, we used log average weekly MME as our dependent variable. The percentage change in log MME per one unit increase in the uncensored, or latent variable was

measured using:

$$\log(MME)^* = \beta_0 + \beta_1 Time + \beta_2 (Time - t^*) + \zeta + error^1$$

where $\log(MME)^*$ is the latent, uncensored variable, time is the number of weeks, t^* is the spline knot for the intervention start, and ζ is the clinician random effect.¹ We adjusted the coefficients by calculating the average partial effect to interpret not just the linear change in $\log(MME^*)$, but the non-linear likelihood that $\log(MME^*)$ is uncensored, resulting in comparable estimates to ordinary least squares.²

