5.2 Handling of Study Interventions

The following interventions will be tested: *Accountable Justification (AJ)* is an EHR-based intervention that will prompt the clinician to justify, in a free text response, the decision to prescribe an opioid or to not reduce high risk/high dose prescribing. The prompt is designed to inform the clinician that the justification will be seen by others in the patient's medical record as an "High risk prescribing justification" note, and that if no justification is entered, the phrase "no justification given" will appear in the note.

Delivery of AJ nudges in Epic's electronic health record (EHR) based on patient type is described below.

Opioid-naïve: An automated search of EHR data determines whether the patient received an opioid prescription within 90 days. If no opioid was prescribed, the clinician receives an alert cautioning against initiating a prescription based on current guidelines. The clinician can either remove or continue with the current opioid prescription. The former results in return to normal workflow after receiving a prompt recommending physical therapy and non-opioid alternatives. The latter, however, induces a prompt requiring the clinician to justify their decision in free text. A Justification Note with the clinician's response is recorded in the Visit Summary portion of the patient's record. A generic "No justification given" is generated for blank responses.

At-risk for long term use: If an automated search of EHR data reveals an opioid prescription(s) within 90 days of the current order, but no previous opioid prescription prior to 90 days before, a prompt explaining the danger of continuing refills based on current guidelines appears. The process is otherwise the same as above; clinicians who cancel a prescription receive a prompt recommending non-opioid alternatives and physical therapy, whereas those who continue with the order are required to justify their decision.

Long term opioid recipient: If an automated search of EHR data reveals total opioid doses are at least 50 MME per day, there are two or more prior opioid prescriptions with two different start dates both greater than 1 day and less than 91 days, and there is a prior opioid prescription with a start date greater than 90 days and less than 181 days, a prompt suggesting an opioid taper appears.

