9.1 General Design Issues

Hypotheses

Our primary hypothesis is that clinicians receiving behavioral economic interventions will have lower opioid prescribing rates post-intervention as compared to baseline. We will estimate weekly milligram morphine equivalent for each clinician and observe the change each month. This will capture CDC guideline prescribing endpoints.

Design

The Application of Economics & Social psychology to improve Opioid Prescribing Safety (AESOPS) R21 is a pilot study to test the feasibility of clinical decision support nudges within the electronic health record to discourage unnecessary opioid prescribing through the application of "behavioral insights"— empirically-tested social and psychological interventions that affect choice. Over a 34 week study period, participating clinicians will receive any of three nudges when eligibility criteria are met within a patient's chart: 1) **Opioid naïve**: Visit where the order is for an included opioid and there is no prior opioid prescription with a start date of greater than 1 day and less than 91 days, 2) **At-risk for long term use**: Visit where the order is for an included opioid there is a prior opioid prescription with a start date greater than 1 day and less than 91 days, and there is no prior opioid prescription with a start date greater than 90 days, and 3) **Long-term opioid recipient**: Total opioid doses are at least 50 MME per day, there are two or more prior opioid prescriptions with two different start dates both greater than 1 day and less than 91 days, and there is a prior opioid prescription with a start date greater than 90 days and less than 181 days.

Outcome Measures

The primary outcome is change in weekly milligram morphine equivalent from baseline to post intervention period. We will estimate weekly milligram morphine equivalent for each clinician and observe the change each month. This will capture CDC guideline prescribing endpoints.

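### The outcome is a baseline-to-post change in weekly MME, but the model marks the intervention only by a slope change at go-live and no primary contrast is named, so an immediate fall may be missed or confused with prior trend

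*Combined protocol and SAP*

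**What the plan says.** Section 9.1 defines the outcome as a difference between periods: "The primary outcome is change in weekly milligram morphine equivalent from baseline to post intervention period". Its hypothesis likewise expects lower prescribing after the intervention than before it. Section 10 repeats the comparison: "We assessed change in average per-clinician weekly MME from the 34-week baseline period before, to the 34-week period post-intervention".

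Section 10 then specifies a left-censored mixed model for log weekly MME: "Predictors include the fixed effects time in weeks, time with a knot at the intervention start, and a random intercept for clinician". There is no indicator for the post period. The spline is justified by the need to allow for "a non-linear change in the rate of opioid prescribing from baseline to post-intervention". After fitting, "We adjusted the coefficients by calculating the average partial effect", which rescales the terms already in the model and adds none. No sentence says which coefficient or fitted contrast answers the primary question.

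Two other parts of the plan bear on how fast an effect might appear. In Section 5.2 the opioid-naïve alert acts on the order in front of the clinician: "The clinician can either remove or continue with the current opioid prescription". The at-risk alert works the same way: "clinicians who cancel a prescription receive a prompt recommending non-opioid alternatives and physical therapy". For long-term recipients, Section 5.2 describes a prompt towards tapering, and Section 9.5 words the inferential hypothesis around that group: "our primary hypothesis is that milligram morphine equivalent dose will decrease for persons on high doses of opioid therapy". Section 9.2 confirms one clinic and no randomization.

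**The concern.** A between-period change and a change in slope are different quantities. They agree only if the effect starts at zero at go-live and grows steadily. With no level term, a drop in the first intervention week has no parameter of its own, and the fit must spread it over the terms it has.

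Two analysts following this plan could report different results from the same data. One would give the slope change and might conclude that nothing happened. The other would give the difference in fitted period means and report most of the fall, but could not separate it from a decline already under way. The pilot is meant to lead to a cluster randomized trial, so a fall at go-live that is misread as prior trend would misinform that step.

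**Working it through.** **Inputs.** From Sections 3 and 10: 34 baseline weeks, 34 intervention weeks, 41 clinicians, and terms for time, knotted time and a clinician intercept. Assumed, because the documents give no effect size, SD or share of zero weeks: a 30% fall, D = ln(0.7) = -0.357. The plan gives no power or effect figure to reproduce. Weeks are numbered 1 to 68, go-live lies at 34.5, u = week - 34.5, and the knotted term is max(0, u).

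**1. Immediate sustained step, planned model (least-squares projection).** max(0, u) = (u + |u|)/2, so the model spans 1, u and |u|. A step at go-live is D/2 + (D/2)·sign(u). Since sign(u) is odd, it is orthogonal to 1 and |u|, so:
- β2 = 0 for any D.
- β1 = (D/2)·Σ|u|/Σu² = (-0.357/2) × 1156/26197 = -0.0079 per week. This is a decline running through a baseline that was in fact flat.
- Fitted post-minus-baseline difference = 34·β1 = -0.268, and -0.268/-0.357 = 75%.

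With the knot at week 34 or 35, β2 over 34 weeks is -0.016 or +0.016.

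**2. Pure secular trend.** A steady -0.0079 per week with no intervention effect gives β2 = 0 and a fitted difference of -0.268, the same fitted line as the step.

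**3. Gradual falls (linear to the full fall over L weeks, then held; knot 34.5).** Two ways of expressing β2 are shown. One is its mean post-period contribution (17·β2) as a share of the true mean difference. The other is 34·β2 as a share of the full fall.

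| Shape | 17·β2, share of mean difference | 34·β2, share of full fall | Fitted difference, share of mean difference |
|---|---|---|---|
| Step | 0% | 0% | 75% |
| 8 weeks | 34% | 59% | 83% |
| 12 weeks | 49% | 81% | 87% |
| 17 weeks | 67% | 100% | 92% |
| 34 weeks | 100% | 100% | 100% |

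For the 17-week ramp the true mean difference is 0.75 × -0.357 = -0.268 and β2 = -0.0105 per week. Then 17·β2 = -0.178, which is 67% of -0.268, and 34·β2 = -0.357, which is 100% of the full fall. The ramp shares therefore depend on the metric; the zero for a step does not.

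**4. Unequal periods.** Sections 4.1 and 9.4.1 speak of six months. With 26 post weeks, β2 recovers 15–21% of a step on the first metric and 31–40% on the second, so the exact zero belongs to the 34 + 34 layout.

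**5. Censoring.** Large-sample random-intercept left-censored fits (assumed residual SD 1.5, clinician SD 0.7; 5%, 21% and 40% of baseline weeks censored) gave β2 over 34 weeks of -0.002, -0.004 and -0.010 for the step. The fitted difference was again 75%.

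**6. With a post-period indicator.** The average departure from the extrapolated baseline trend, β3 + 17·β2, recovers 100% for every shape above if the baseline is linear (99–100% in the censored fits). The SE of β2 is unchanged (ratio 1.00). The SE of the average departure is 1.48 to 1.57 times that of the mean slope contribution, for knots from 34 to 35.

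**7. Power, illustration only** (independent weeks, residual SD 1.5, 41 clinicians, two-sided 5%).

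| Shape | Average departure, level model | β2 | Fitted difference, planned model |
|---|---|---|---|
| Step | 66% | 5% | about 100% |
| 34-week ramp | 22% | 44% | about 95% |

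For a 17-week ramp the first two are about equal (43% and 44%). The last column is high partly because that contrast also responds to any secular trend.

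**The case against.** The strongest reply is that a slope was intended. Section 10 says the between-period change was assessed by means of the spline, to allow for a changing rate, and it describes the measured quantity in terms of change per unit increase, which is the language of a coefficient. Sections 9.1 and 9.4.1 also track change month by month, and a drop at go-live would be visible there. The Section 9.5 hypothesis concerns high-dose patients. Their prompt is about tapering, and Sections 7.1 and 7.3 treat abrupt drops as safety matters, so a gradual response is the natural expectation in that group. This is also a one-clinic feasibility pilot with no sample-size target, and a level term cannot establish causation.

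Much of this stands. A reader might infer that the slope has no connection with the stated outcome, or that the plan commits itself to β2 and will therefore miss the effect. The documents support neither: Section 10 ties the spline to the between-period change, and it never names β2 as the effect. A slope target is a legitimate choice, and a linear 34-week build is recovered in full.

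The choice is still not stated. The opioid-naïve and at-risk alerts can remove an order on the day, so an immediate component is plausible. The split of MME across the three patient types is not given, so neither shape can be ruled out. The monthly series is descriptive and does not replace a named contrast.

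**Conclusion.** The point holds in a conditional form and should be fixed. The outcome is worded as a between-period change, the model allows only a change of slope at go-live, and the primary contrast is unnamed. If β2 is the effect, an immediate sustained fall of any size yields about zero and is displayed as a baseline trend. If the fitted difference is the effect, 75% of the step appears but cannot be told apart from a secular trend.

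The step result rests on equal 34-week periods, a knot at go-live and a flat underlying series; it does not depend on effect size or variance. The ramp shares depend on ramp length and metric, and the power figures rest on assumed SDs and independence. A reader might go further and infer that the planned model fails for any rapid effect, or that adding a level term would isolate the intervention. Neither follows: ramps are partly or fully recovered, and in a single-arm series the level term picks up anything else that changed at go-live.

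**What to change.** - Add β3·Post to the Section 10 model, with Post = 1 from go-live. Report this level-plus-slope model beside the planned one, with confidence intervals for the level change, the slope change and the average post-period difference from the extrapolated baseline trend.
- State which contrast answers the primary question and why, and reconcile the rate wording in Section 10 with the baseline-to-post wording in Sections 9.1 and 10.
- Section 10 is written in the past tense. If the slope-only model has already been run, label the added model as later.

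The cost is one model term and some wording. β2 loses essentially no precision. The average difference is less precise (SE about 1.5 times that of the mean slope contribution), has less power than β2 for effects that build over more than about 17 weeks, and relies on extrapolating a linear baseline across 34 weeks. Which contrast is primary is therefore for the investigators to decide and record.

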3. STUDY DESIGN

The Application of Economics & Social psychology to improve Opioid Prescribing Safety (AESOPS) pilot study involves 41 Northwestern Medicine clinicians for which the primary aim is to test the feasibility of three interventions based on behavioral economic principles to reduce the reliance on opioids and encourage safe and effective pain management. The study period includes a 34 week baseline period and 34 week study intervention period. The primary outcome is average weekly morphine milligram equivalents (MME) prescribed per-clinician.

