6.2.2 Enrollment, Baseline, and/or Randomization

Enrollment

Eligible clinicians from one pilot clinic will receive study interventions.

Baseline Assessments

None

Randomization

None

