9.2 Sample Size and Randomization

Not applicable as this is a pilot feasibility study within one clinic with no randomization.

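### The Section 10 model leaves out variation shared by all clinicians in a calendar week, so any such variation makes the standard error of the post-knot slope too small, by an amount the documents do not determine

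*Combined protocol and SAP*

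**What the plan says.** Section 10 (Statistical Analysis) defines the outcome at clinician-week level: "The primary outcome is average weekly morphine milligram equivalents (MME) prescribed per-clinician". The predictors are listed in full: "Predictors include the fixed effects time in weeks, time with a knot at the intervention start, and a random intercept for clinician". The displayed equation has one error term and one random term, which "is the clinician random effect". Estimation is by maximum likelihood: "The density function to achieve maximum likelihood estimates for a left censored regression".

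On design, Section 3 states that the "pilot study involves 41 Northwestern Medicine clinicians" and that "The study period includes a 34 week baseline period and 34 week study intervention period". Section 6.2.2 says "Eligible clinicians from one pilot clinic will receive study interventions", and Section 9.2 answers the sample-size and randomization item with "Not applicable as this is a pilot feasibility study within one clinic with no randomization".

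The plan describes no calendar-week effect, seasonal term, serial-correlation structure, week-clustered or bootstrap standard error, or sensitivity analysis on this point. It states neither alpha nor the sidedness of the test.

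**The concern.** The intervention effect is the change in slope at the knot. The regressor that carries it varies over weeks but not between clinicians. Anything that moves prescribing for the whole group in a given week therefore falls on that regressor undiluted, and averaging over 41 clinicians does not reduce it. The likelihood counts such a movement as up to 41 separate pieces of evidence. The clinician intercept cannot absorb it, because that intercept is constant over time.

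Holiday weeks are a plausible source. The two periods together cover 34 + 34 = 68 weeks, more than a year, so if they run consecutively, as the single knot implies, every calendar date falls in the window. The documents record no particular closure, holiday effect or policy notice.

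At stake are the width of the confidence interval and the validity of the test for the primary hypothesis in Section 9.1. With no concurrent control, the standard error of the slope change is the main protection against reading chance weekly movement as an effect.

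**Working it through.** The plan gives no power, alpha or standard error on this point, so there is no figure to reproduce.

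**Inputs from the documents**
- Clinicians: 41 (Section 3).
- Weeks: 34 + 34 = 68 (Section 3). Clinician-weeks if complete: 41 × 68 = 2,788.
- Model terms: week, week after the knot, clinician random intercept (Section 10).

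**Assumptions**
- Two-sided test at 5%.
- rho, the fraction of within-clinician weekly variance common to all clinicians in a week: varied from 0 to 0.10.
- The knot term is zero before the intervention. The equation is printed without that truncation, and read literally its time terms are collinear (design rank 2 of 3).

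**Step 1: variance of a weekly mean.** With balanced data and regressors that vary only by week, the slope estimate depends only on the 68 weekly means. Let sigma² be the within-clinician weekly variance.
- Variance the model assumes for a weekly mean: sigma²/41.
- Actual variance: sigma²[(1 − rho)/41 + rho] = (sigma²/41)(1 + 40 rho).

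The ratio of true to reported SE is therefore sqrt(1 + 40 rho). The type I error is 2 × [1 − Phi(1.96 / sqrt(1 + 40 rho))].

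**Step 2: numbers, for shocks independent from week to week**

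| rho | 1 + 40 rho | SE ratio | Type I error |
|---|---|---|---|
| 0 | 1.0 | 1.00 | 5.0% |
| 0.005 | 1.2 | 1.10 | 7.4% |
| 0.01 | 1.4 | 1.18 | 9.8% |
| 0.02 | 1.8 | 1.34 | 14.4% |
| 0.04 | 2.6 | 1.61 | 22.4% |
| 0.05 | 3.0 | 1.73 | 25.8% |
| 0.10 | 5.0 | 2.24 | 38.1% |

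**Step 3: simulation under no effect (41 × 68)**
- Uncensored random-intercept model, 4,000 runs per setting: 4.3%, 7.8%, 9.3%, 14.7%, 26.2% and 37.9% at rho = 0, 0.005, 0.01, 0.02, 0.05 and 0.10.
- Left-censored model with about 31% zeros, clinician intercepts fitted as fixed effects to approximate the random intercept, 600 runs per setting: 5.3%, 10.7%, 14.7%, 24.0% and 38.0% at rho = 0, 0.01, 0.02, 0.05 and 0.10. Censoring does not remove the problem.

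**Step 4: does clustering on clinician help?** With residual SD 1 and shared-shock SD 0.1 or 0.2, rho is 0.01/1.01 = 0.0099 or 0.04/1.04 = 0.038. Clinician-clustered standard errors gave 10.1% and 22.0%, against 10.1% and 21.8% for the random-intercept model. They do not help.

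**Step 5: does an independent week effect help?** Testing the slope on the 68 weekly means, with 68 − 3 = 65 degrees of freedom, gave 4.5% to 5.5% for rho from 0 to 0.10 when shocks were independent across weeks. With serially correlated shocks (AR(1) 0.5, assumed) and rho = 0.05, the stated model gave 46.0% and the week-level test still gave 20.4%. At rho = 0.01 the week-level test gave about 12%.

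**Step 6: several clinics.** If shocks were specific to clinics of about 10 clinicians each (assumed) with rho = 0.01 within clinic, the factor would be 1 + 9 × 0.01 = 1.09, the SE ratio 1.04 and the type I error 6.0%.

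**The case against.** The strongest reply is that nothing in the documents fixes rho. At rho = 0 there is no inflation, and the plausible range runs from negligible to serious. That stands. A reader might infer that the primary test has a false-positive rate of 10% or 22%. The documents support only the mechanism and its direction.

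A reader might also infer that the trial holds just 68 independent data points. That goes too far. Under the formula above, the effective number is 2,788/1.4, about 1,991 clinician-weeks, at rho = 0.01 and 2,788/2.6, about 1,072, at rho = 0.04.

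The one-clinic reading is not fully settled. Sections 6.2.2 and 9.2 say one clinic, whereas the inclusion criteria in Section 4.1 refer to study clinics in the plural within one site. Closures or staffing problems confined to one clinic would matter less (Step 6). Calendar effects would still be shared by everyone.

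The outcome definition also matters. If weekly MME is a per-visit average rather than a weekly total, swings in visit volume count for less, except through more zero weeks. The text does not say which it is.

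Finally, this is an unrandomised feasibility pilot with no stated alpha or success rule. That limits the consequences but does not remove the point: Section 9.1 states a directional primary hypothesis, Section 9.5 announces inferential analysis, and the précis says the nudges go on to a cluster randomized trial.

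**Conclusion.** The concern holds as a statement about the model as written. Time varies only by week, the sole random effect is the clinician intercept, and all clinicians share one start date without a control. Any positive shared weekly variation therefore makes the model-based standard error of the post-knot slope too small, and clinician-clustered errors leave the problem in place.

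The size is conditional. With a two-sided 5% test and week-to-week independent shocks common to all 41 clinicians, a shared fraction of 1% roughly doubles the type I error. Serial correlation makes it worse, and shocks confined to separate clinics make it milder. Confidence is high for the mechanism only. Taking model-based maximum likelihood errors as the plan's choice is the natural reading of Section 10, though the type of standard error is not stated.

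**What to change.** In Section 10, state that the standard error and test of the post-knot slope will rest on week-level variation and allow for serial correlation. Either of two routes would do:

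- a bootstrap that resamples blocks of consecutive weeks, keeping all clinicians together, around the stated censored model; or
- a calendar-week random effect crossed with the clinician intercept, with an autocorrelated structure such as AR(1).

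An independent week random intercept is the minimum. It is not interchangeable with the two routes above (Step 5), so the plan should check week-level residuals for autocorrelation before relying on it. Sections 4.1, 6.2.2 and 9.2 should also agree on whether there is one clinic or several, and alpha and sidedness should be stated.

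These steps correct the standard error only. Adjacent 34-week periods cover different parts of the year, and the resulting seasonal bias remains.

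No new data are needed. With independent shocks the confidence interval widens by about 18% at rho = 0.01 and 61% at rho = 0.04 (SE ratios 1.18 and 1.61). A crossed week effect makes the censored likelihood and the average partial effects harder to compute. Because Section 10 is written in the past tense, the change may have to be made as a re-analysis. If shared variation is negligible, the result will barely change.

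### A clinician random intercept is the only correlation term over up to 68 weeks, so model-based precision for the slope change may be too small or too large

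*Combined protocol and SAP*

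**What the plan says.** Section 3 sets the scale: the "pilot study involves 41 Northwestern Medicine clinicians", and "The study period includes a 34 week baseline period and 34 week study intervention period". That is 34 + 34 = 68 weeks per clinician and at most 41 x 68 = 2,788 clinician-weeks.

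Section 10 gives the outcome ("The primary outcome is average weekly morphine milligram equivalents (MME) prescribed per-clinician") and the only model for it, a mixed-effects censored regression of log weekly MME. It compares the "34-week baseline period before, to the 34-week period post-intervention". The predictors are time in weeks, "time with a knot at the intervention start, and a random intercept for clinician". In the equation "ζ is the clinician random effect", and one error term with a single variance follows it. Estimation is by maximum likelihood, and the coefficients are then converted to average partial effects.

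The document names no random slope, serial error structure, robust or clustered variance, bootstrap, or sensitivity analysis for correlation. It also states no interval, significance level or test for the slope change. Section 9.5 does announce an inferential analysis, and Section 9.1 states a directional primary hypothesis.

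On design, Section 9.2 describes a "pilot feasibility study within one clinic with no randomization", and Section 6.2.2 says "Eligible clinicians from one pilot clinic will receive study interventions".

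**The concern.** A random intercept absorbs differences in level between clinicians. It treats any two weeks of the same clinician as equally correlated, whether one week or a year apart. Standard errors read from the fitted likelihood are assured to be right when weeks are independent given the intercept and the slope change at the knot is common to all clinicians. The second condition matters only if the target extends beyond these 41 clinicians.

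Neither condition is obvious here. Long-term recipients are defined by repeated prescriptions, so orders recur in time. Spaced refills can produce negative correlation and standard errors that are too large. Patient turnover or clinician absence can make them too small. The nudge works through each clinician's own judgement, so responses may differ.

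At stake is the precision attached to the pilot's only outcome, for which Section 10 is the only model.

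**Working it through.** **Inputs from the document:** 41 clinicians, 34 baseline weeks and 34 intervention weeks. The plan gives no standard deviation, autocorrelation, slope variation, significance level or sample-size figure, so there is no figure of its own to reproduce. Everything else below is assumed, including the two-sided 5% test. The knot term is read as zero before the intervention start, as the word knot implies, although the printed equation does not show the truncation.

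**Linear approximation.** Let t = 1 to 68, k = max(t - 34, 0), X = [1, t, k], and let a be the row of (X'X)^-1 X' that yields the coefficient of k.

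- True variance of the slope change: a'Va / 41, where V is the within-clinician covariance over weeks.
- Model-based variance: s^2 a'a / 41, where s^2 is the expected pooled within-clinician residual mean square and a'a = 0.000611.
- Ratio = true SE / model-based SE.
- Actual rejection of a nominal 5% test = 2 x (1 - Phi(1.96 / ratio)).

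With unit variance and independent weeks, both standard errors are sqrt(0.000611 / 41) = 0.00386 and the ratio is 1.

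Serial correlation with first-order autoregressive errors:

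| Lag-1 correlation | Ratio | Rejection |
|---|---|---|
| -0.3 | 0.74 | 0.8% |
| -0.2 | 0.82 | 1.7% |
| -0.1 | 0.91 | 3.1% |
| 0.1 | 1.10 | 7.5% |
| 0.3 | 1.35 | 14.6% |
| 0.5 | 1.70 | 24.8% |

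For example, at -0.2 the standard errors are 0.00318 / 0.00387 = 0.82, and at 0.3 they are 0.00517 / 0.00383 = 1.35.

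Slope change varying between clinicians (target beyond these 41): add SD^2 kk' to V, with residual SD 1.5. For SD 0.01 / 0.02 / 0.03 log units per week, the ratio is 1.03 / 1.12 / 1.26 and rejection is 5.8% / 8.1% / 11.9%.

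Both together: SD 0.02 with correlation -0.2 gives 0.00570 / 0.00587 = 0.97. The two departures nearly cancel.

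**Does it carry over to a censored model?** A random-intercept censored regression was simulated with about 36% zero weeks and 150 runs per setting. The ratio was 1 / 0.989 = 1.01 under independence and 1 / 0.743 = 1.35 at correlation 0.3, with 19% rejection. At -0.2 the spread of the estimates fell to 0.120 from 0.144, but at least one run gave no usable standard error, so no ratio is available there. A separate censored fit with clinician fixed intercepts (200 runs per setting) on simulated refill data gave 0.69 to 0.86 for stable panels, 1.13 to 1.17 with turnover and 1.12 to 1.28 with absences. Both directions therefore occur under censoring too.

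**Refill simulation.** The setup was 41 x 68, no true effect, refills about every 4 weeks, a linear fit and 1,000 runs per setting. The outcome was taken as log(1 + total weekly MME).

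| Settings | Ratio | Model-based rejection |
|---|---|---|
| Stable panels (3) | 0.62 to 0.82 | 0.1 to 1.5% |
| Turnover (4) | 1.08 to 1.17 | 7.4 to 9.1% |
| Stable panels with 3-week absences (2) | 1.24 to 1.39 | 12.1 to 15.6% |

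A clinician-clustered test with t on 41 - 1 = 40 df rejected 3.9 to 6.2% in all nine settings. In the turnover settings the lag-1 correlation was -0.10 to -0.17, yet the model-based errors were too small, so lag-1 correlation alone does not settle the direction.

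**What clustering does not cover.** In a censored-model run with correlation 0.3, where 2% of residual variance was a weekly shock shared by all clinicians, the clustered test still rejected 10%, against 22% model-based.

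**The case against.** The strongest reply is that the plan never says which standard error it will use. It specifies no interval, test or significance level, and silence does not commit it to model-based errors. That stands, and it makes the point conditional. But an inferential analysis is announced and Section 10 is its only model, so model-based output is what an analyst following the text would naturally report.

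The illustrations do not describe this trial. Every input beyond 41 clinicians and 34 + 34 weeks is assumed, and the autoregressive rows at 0.3 and 0.5 lie outside the lag-1 range of the refill simulation (-0.25 to +0.25). The simulation also takes total weekly MME as the outcome. Section 4.1 speaks of visits in an outcome denominator and Section 10 of weeks with a zero average, so MME averaged over visits is possible, and refill timing would then act differently. All of this stands, and the figures show only that either direction is possible.

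Clustered standard errors are not a full remedy. Misspecified correlation in a censored random-effects model can also affect the point estimate, and correct test size under no effect does not show that a non-zero effect is estimated without bias. This stands and shapes the fix.

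Finally, this is a feasibility pilot with no go/no-go rule tied to the estimate. That stands and limits the weight of the point.

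**Conclusion.** The point holds in conditional form. If standard errors, intervals or p-values for the slope change or the average partial effects are taken from the Section 10 model, they may be too small or too large. The documents do not allow direction or size to be determined. The ratios of 0.82 and 1.35 are illustrations from a linear approximation under assumed correlations.

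A reader might infer two stronger things. One is that the standard errors are too small, so that a fall in prescribing would be declared too readily. The documents give no autocorrelation, and regular refills by stable patients can push the error the other way. The other is that precision must be wrong unless both conditions hold. The 0.97 case shows that departures can offset, and the common-slope condition drops out if the target is these 41 clinicians.

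The consequence is confined to the precision reported for a pilot's effect estimate, so this is a minor point.

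**What to change.** 1. Base any interval or test for the slope change and the average partial effects on clinician-clustered (sandwich) standard errors with a t reference on 40 df, or on a bootstrap that resamples whole clinicians. Carry the average-partial-effect step through the same procedure.
2. Add one sensitivity fit with a clinician-random slope change, or with serial correlation, to see whether the point estimate moves.
3. State whether the target is these 41 clinicians or clinicians more widely.
4. State as a limitation that neither variance method covers weekly shocks shared by all clinicians at the single site.

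The cost is a variance option or a bootstrap loop and one extra model fit, with no new data. Intervals may widen or narrow, and they can remain too narrow if clinicians share weekly shocks.
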